11.3.2 Hypothesis, analysis methods and performance requirements

The null hypothesis that will be tested is that the hazard ratio for aCRT versus control is equal to 1. It will be tested against the alternative hypothesis that the hazard ratio is unequal to 1.

Let $S_T(t)$ and $S_C(t)$ denote the proportion of patients in the treatment arm and control arm, respectively, that have not experienced a primary endpoint up to time t . Let $h_T(t)$ and $h_C(t)$ be the associated hazard functions. Under the proportional hazards model, $h_T(t) = HR h_C(t)$, where HR is the hazard ratio of treatment compared to control. The null and alternative hypotheses can be expressed as:

$$H_0 : HR = 1$$

$$H_A : HR \neq 1$$

The hypothesis will be tested using a Cox proportional hazards regression model with a random center effect (frailty), stratified by baseline NYHA class. The hazard ratio for treatment arm versus control arm will be reported with its associated p-value and 95% confidence interval. The null hypothesis will be rejected when the p-value is below the critical value for the (interim or final) analysis, and it will be concluded that aCRT reduces the incidence of the primary endpoint when the hazard ratio is below 1. Kaplan-Meier graphs for incidence will also be reported, together with an estimate for the absolute event rate difference at 2 years post randomization.

Two further analyses of the primary objective are planned. First, a Cox regression model will be reported with a random center effect and a risk score as fixed effect. The risk score will be derived from baseline data. Second, an analysis will be done including only the patients for whom the ECG Core Laboratory confirmed the presence of LBBB.

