4.3.2 Analysis Methods

The hypothesis will be tested using a Cox proportional hazards regression model with a random site effect (frailty), stratified by NYHA class at enrollment. In this combination of stratified Cox regression and frailty model, the hazard for subject i from site j with NYHA class k at enrollment is:

$$\lambda_{ijk}(t) = \lambda_{0k}(t) \xi_j \exp(\beta X_{ijk})$$

where $i = 1, \dots, n$; $j = 1, \dots, J$; $k = 1, 2, 3$.

$\lambda_{0k}(t)$ is the baseline hazard of k^{th} NYHA class. This is the part of stratified Cox regression, where the baseline hazards of NYHA class play no role in the estimation of treatment effect. That is, no between-NYHA-class comparisons of treatment effect are attempted and all information about the treatment effect comes from within NYHA class comparisons. ξ_j ($j = 1, \dots, J$) are frailties or site effects that follow a gamma distribution with mean 1 and variance θ_0 independently and identically. The variance parameter θ_0 is a measure of the heterogeneity across sites in baseline risk. As θ_0 increases, the values of ξ_j become more dispersed, inducing greater heterogeneity in the site-specific baseline hazards. This is the part of random effects or frailty model.⁷ Therefore, $\xi_j \lambda_{0k}(t)$ is the baseline hazard of k^{th} NYHA class at j^{th} site, and ξ_j is constant for $k = 1, 2, 3$ NYHA class from the same site j . X_{ijk} is the randomization assignment (ACRT ON or ACRT OFF), and $\exp(\beta)$ is the hazard ratio for treatment.

The SAS PHREG procedure will be used to conduct the survival analysis of primary endpoint using code similar to:

```
PROC PHREG DATA=primary;
  CLASS NYHA site;
  MODEL time*event(0) = rand / TIES=efron;
  STRATA NYHA;
  RANDOM site/ dist = gamma;
RUN;
```

Event = 1 when a subject experienced an event that was adjudicated as primary endpoint (intervention for HF decompensation or death). Event = 0 when a subject did not experience a primary endpoint, and therefore was censored. Time to event starts from the date of randomization and ends at the date that the event occurs for those who experience

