the event or the date of last documented follow-up since randomization for those who are censored. Date of last documented follow-up since randomization is the maximum value among the dates of randomization, randomization programming, any study scheduled follow-up visit, exit, adverse event onset, adverse event resolved, system modification, and healthcare utilization. Rand is an indicator variable for randomized treatment groups (1=aCRT ON, 0=aCRT OFF).

The hazard ratio for treatment arm (aCRT ON) versus control arm (aCRT OFF) will be reported with its associated p-value and 95% confidence interval. The null hypothesis will be rejected when the p-value is below the critical value for the (interim or final) analysis. The actual cumulative α level will be calculated based on the actual number of primary events included in each interim analysis. The estimated cumulative α -level is approximately 0.00002, 0.00304, 0.0193 and 0.05 at the 1st interim with 275 events, 2nd interim with 550 events, 3rd interim with 825 events and the final analysis with 1100 events, respectively (see details in section 0). It will be concluded that aCRT reduces the incidence of the primary endpoint when the null-hypothesis is rejected and the hazard ratio is below 1. Kaplan-Meier plots for incidence of primary endpoint will be presented by treatment arms, for all patients and for the separate NYHA class groups. The absolute event rate difference at 2 years post randomization will also be calculated.

The following model assumptions will be checked:

1. Proportional hazards between treatment arms: an interaction term of treatment arm by time (in log scale) will be added into the model (see the code below). If this interaction effect is not significant, the proportional hazard assumption holds. Otherwise, this interaction term should be kept in the model as a remedy for non-proportional hazards, and any secondary analysis where treatment (or treatment by subgroup factor interaction) is included should also include the corresponding interaction term with time. Being time dependent, the treatment effect will be assessed every 6 months to the end of the follow-up to monitor the direction. Significance of the treatment effect will be based on its estimate at 24 months using a contrast.

```
PROC PHREG DATA=primary;  
  CLASS NYHA site;  
  MODEL time*event(0) = rand rand_t / TIES=efron;  
  rand_t = rand*log(time);  
  STRATA NYHA;  
  RANDOM site/ dist = gamma;  
RUN;
```

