2. Hazard ratio for treatment is constant across NYHA classes: the following code will be used to check this assumption. That is, instead of doing stratified Cox regression, NYHA class will be regarded as a covariate in a frailty model along with the interaction between treatment and NYHA class. If the interaction is not significant and the hazard ratios for treatment are similar at different NYHA classes, the assumption of stratified Cox regression part of the model in primary analysis is valid. If the interaction is significant, the assumption does not hold, and we will consider NYHA class as a covariate instead of a stratification factor in the frailty model for primary analysis and other relevant analyses, and keep the interaction term in the model. The treatment effect will be reported separately for the different NYHA classes.

```
PROC PHREG DATA=primary;  
  CLASS NYHA(ref='NYHA class II') site rand(ref=0)
```

```
        / param=ref order=internal;  
MODEL time*event(0) = rand NYHA rand*NYHA / TIES=efron;  
RANDOM site/ dist = gamma;  
HAZARDRATIO rand / diff=all at (NYHA='NYHA class II');  
HAZARDRATIO rand / diff=all at (NYHA='NYHA class III');  
HAZARDRATIO rand / diff=all at (NYHA='NYHA class IV');  
RUN;
```

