4.3.5 Subgroup Analysis: Interaction with Treatment

Subgroup analysis of the primary endpoint will follow the ITT principle and include all randomized patients. The purpose is to test if the effect of aCRT treatment on primary endpoint would vary by pre-specified subgroup factors including:

- Geography: US/Canada vs. International
- Age
- Gender: Males vs. Females
- QRS duration: ≤ 150 ms vs. > 150 ms
- AV conduction time: median as cutoff
- LBBB: Core Lab confirmed vs. Core Lab not confirmed
- NYHA class (in different model where NYHA class is a covariate not a stratification factor)
- HF etiology
- Renal dysfunction
- Diabetes

This analysis will be conducted by adding subgroup and its interaction with treatment into the model used for the primary analysis. The codes will be similar to:

```
PROC PHREG DATA=primary;  
  CLASS NYHA site subgroup;  
  MODEL time*event(0) = rand subgroup rand*subgroup / TIES=efron;  
  STRATA NYHA;  
  RANDOM site/dist = gamma;  
RUN;
```

The treatment by subgroup interaction effects will be tested at $\alpha=0.05$. P values will not be adjusted for multiplicity. The significance of interaction effects and confidence intervals of hazard ratios for subgroups will be presented in a Forest plot.

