4.4.1 Secondary Objective #1: All-cause mortality

The secondary objective #1 is to test the hypothesis that aCRT ON reduces all-cause mortality compared to aCRT OFF. All-cause mortality is one of the two components that comprise the primary endpoint.

Hypothesis

Let $S_T(t)$ and $S_C(t)$ denote the proportion of patients in the treatment arm (aCRT ON) and control arm (aCRT OFF), respectively, that have not died up to time t . Let $h_T(t)$ and $h_C(t)$ be the associated hazard functions. Under the Cox regression model that assumes proportional hazards, $h_T(t) = HR \cdot h_C(t)$, where HR is the hazard ratio of treatment compared to control. The null and alternative hypotheses are:

$$H_0 : HR = 1$$

$$H_A : HR \neq 1$$

Analysis Method

Similar to the primary endpoint, the hypothesis regarding the aCRT effect on all-cause mortality will be tested using a Cox proportional hazards regression model with a random site effect (frailty), stratified by NYHA class at enrollment. Section 4.3.2 has described this model in details. The analysis will be conducted using code similar to:

```
PROC PHREG DATA=mortality;  
  CLASS NYHA site;  
  MODEL time*death(0) = rand / TIES=efron;  
  STRATA NYHA;  
  RANDOM site/dist = gamma;  
RUN;
```

In these codes, death = 1 given an adjudicated death and death = 0 otherwise; time to death starts from the date of randomization and ends at the date of death for those who die, or the date of last documented follow-up since randomization for those who are censored. Date of last documented follow-up since randomization is the maximum value among the dates of randomization, randomization programming, any study scheduled follow-up visit, exit, adverse event onset, adverse event resolved, system modification, and healthcare utilization.

The model assumptions will be checked using the same methods that are described in detail in section 4.3.2 for the primary endpoint. That is, the assumption of proportional hazards between the treatment arms will be checked by testing the significance of treatment by time interaction term; and, the assumption of constant hazard ratio for treatment across NYHA classes will be checked by testing the significance of treatment by NYHA class interaction and evaluating the hazard ratio for treatment within each NYHA class.

Missing Data

Similar to the analysis for primary endpoint, we assume non-informative censoring for lost to follow up in the analysis of all-cause mortality.

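### When the treatment-by-NYHA check is significant, SAP 4.3.2 replaces the stratified primary model but names no test that decides H0: HR = 1 in the replacement

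*SAP*

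**What the plan says.** The null hypothesis is a single hazard ratio equal to 1 (SAP 4.3.1). SAP 4.3.2 names the test: "The hypothesis will be tested using a Cox proportional hazards regression model with a random site effect (frailty), stratified by NYHA class at enrollment". Protocol 11.3.2 agrees: "The hypothesis will be tested using a Cox proportional hazards regression model with a random center effect (frailty), stratified by baseline NYHA class". One p-value is compared with the critical value of the stage. Benefit is concluded "when the null-hypothesis is rejected and the hazard ratio is below 1".

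SAP 4.3.2 then lists two assumption checks.

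- **Item 1, proportional hazards.** If the treatment-by-time interaction is significant, it stays in the model and the deciding result is named: "Significance of the treatment effect will be based on its estimate at 24 months using a contrast".
- **Item 2, constant hazard ratio across NYHA classes.** If the treatment-by-NYHA interaction is significant, "we will consider NYHA class as a covariate instead of a stratification factor in the frailty model for primary analysis and other relevant analyses", and the interaction is kept. The item ends: "The treatment effect will be reported separately for the different NYHA classes". The code requests three hazard ratios, one each for class II, III and IV, and no overall contrast. Class II is the reference level, so the coefficient for randomized arm in that code is the class II effect.

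For all-cause mortality, SAP 4.4.1 says "The model assumptions will be checked using the same methods that are described in detail in section 4.3.2 for the primary endpoint". SAP 4.4.2 (heart failure events) and 4.4.4 (atrial fibrillation) reuse the check in the same way.

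**The concern.** Followed literally, item 2 removes the only model in which the primary null hypothesis has a defined test. In the replacement model the plan does not say which coefficient, contrast or joint test meets the critical value, or which hazard ratio must be below 1. It gives no significance level for the check in 4.3.2 and does not say whether the switch applies at interim analyses. It also does not say what happens when both checks are significant.

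The rule behind the trial's main conclusion could therefore be settled after the interaction result is known. The secondary objectives have a related problem. The Hommel procedure in SAP 4.4 needs one p-value per objective, and in this branch objectives #1, #2 and #4 have none unless the stratified test is kept.

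Nothing is gained in return. SAP 4.3.5 already plans NYHA class as a subgroup analysis, in a model with NYHA as a covariate, so class effects can be shown without touching the primary decision.

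**Working it through.** **Inputs from the documents.** SAP 4.3.8: two-sided alpha 0.05, power 90%, HR 0.81818, four equally spaced analyses, O'Brien-Fleming error spending, stopping for efficacy and futility. SAP 4.2: 275, 550, 825 and 1100 events. Allocation is 1:1.

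**Assumptions, not in the documents.** The check is a 2-df test at 0.05, run at the final analysis only. NYHA II/III/IV shares of events are 50/47/3, 40/55/5 or 30/60/10 percent. Site frailty is left out.

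**Step 1: reproduce the plan's figures.**

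- Fixed design: events = 4(z₀.₉₇₅ + z₀.₉₀)² / (ln HR)² = 4(1.960 + 1.282)² / (0.2007)² ≈ 1044.
- Cumulative alpha, spending 0.025 per side and doubling: 0.000015, 0.00305, 0.0193, 0.05. The SAP states 0.00002, 0.00304, 0.0193, 0.05.
- Efficacy bounds |Z|: 4.335, 2.965, 2.360, 1.964. Futility bounds |Z|: none, 0.364, 1.241.
- This design solves to 1103 events at HR 0.81818, against the SAP's 1100. At 1100 events, power is 89.9%.

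**Step 2: model for the branch.** At each look the score for class c is normal with mean θI_c and variance I_c, where I_c = events × share_c / 4 and θ = −ln HR. The stratified statistic is Z = ΣS_c / √ΣI_c. The interaction statistic is Q = ΣS_c²/I_c − Z², referred to chi-square with 2 df. With a common hazard ratio, Q is independent of Z, so the simulated results (2 million draws) can be checked by hand.

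**Step 3: null hypothesis.**

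- If the stratified test always decides, type I error is 5.0%.
- Rejections that first occur at the final analysis: 0.05 − 0.0193 = 0.0307. The check fires in 5% of these: 0.05 × 0.0307 = 0.0015.
- If no overall claim is made in the branch: 0.0500 − 0.0015 = 0.0485. Simulated: 0.0484 to 0.0485.

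**Step 4: common HR of 0.818.**

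- If the stratified test always decides, power is 89.9%.
- The check fires at the final analysis in 1.2% of all trials. This implies that 0.012 / 0.05 = 24% of trials reach that analysis.
- An overall benefit falls in the branch in 1.0% of trials. Without a claim there, power is 0.899 − 0.010 = 0.889.
- If the check also ran at interims, the share would be about 0.05 × 0.899 = 4.5%.

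**Step 5: class effects that differ.** With assumed class II/III hazard ratios of 0.75/0.90, either way round, and 0.82 in class IV, an overall benefit falls in the branch in 3.0 to 5.5% of trials across the assumed shares.

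**Sensitivity to futility.** With the futility bounds ignored, power at HR 0.818 is 90.9% against 89.9%, the branch share is again 1.0%, and the share with class differences is 3.2 to 5.8%.

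**The case against.** **The stratified test may still stand.** Protocol 11.3.2 and the opening of SAP 4.3.2 name it without condition. Item 2 sits under assumption checks, uses a tentative verb, and ends with what is reported rather than what is concluded. This reading is possible, but the sentence refers expressly to the primary analysis and puts the covariate in place of stratification. The Fine-Gray analysis in SAP 4.4.2 describes the same switch in firm terms. Replacement is the plainer reading, and on either reading the plan does not say what decides.

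**Departures must be disclosed.** Protocol 11.1 requires differences between the SAP and the protocol, or between plan and actual analysis, to be explained in the Final Report. That is so, but explaining a choice afterwards is not fixing it beforehand.

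**Carry-over is indirect.** SAP 4.4.1, 4.4.2 and 4.4.4 repeat the check and do not restate the switch. It reaches them through the reference back to 4.3.2 and item 2's mention of other relevant analyses. This stands, and a clarifying clause is enough there.

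**A stronger reading is tempting.** A reader might infer that the primary type I error is inflated, because three class hazard ratios could each be tested. The documents do not support this: they state no rule under which a class result would establish the primary claim.

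**The effect is small.** This stands.

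**Conclusion.** The gap is real. After a significant treatment-by-NYHA check, SAP 4.3.2 puts a different model in the primary analysis and leaves the primary null hypothesis without a named test. The plan meets a higher standard in the adjacent item, where it names a 24-month contrast. That contrast is pre-specified and is not criticised here.

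Its cost is at most about one point of power at the design hazard ratio and a slightly conservative type I error, if the check runs only at the final analysis. The figures rest on an assumed 0.05 level for the check and assumed NYHA event shares. The 3.0 to 5.5% range also needs class hazard ratios that the documents do not give. The point deserves correction because, when the branch occurs, the main conclusion depends on a rule not yet written, and writing it now is cheap.

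**What to change.** In SAP 4.3.2, item 2, replace the sentence on a significant interaction. Adding to it would leave two conflicting instructions. Suggested text:

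> Whatever this check shows, the NYHA-stratified Cox frailty model decides the primary hypothesis at every interim and final analysis. The one exception is a significant proportional-hazards check under item 1: the 24-month contrast from the NYHA-stratified model then decides, also when both checks are significant. The interaction model and the class-specific hazard ratios are supportive and are reported beside the overall result.

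State in SAP 4.4.1, 4.4.2 and 4.4.4 that the same holds where they reuse the NYHA check.

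The cost is a few lines of wording; the same models are still run. It keeps the analysis in protocol 11.3.2 and, under the assumptions above, type I error at 5.0% and power at 89.9%. The downside is interpretive. If effects truly differ by class, the deciding result is an information-weighted average hazard ratio that may describe no single class well, so the class hazard ratios must always appear next to it.

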4.3.3 Missing Data

Follow-up information for all participants is expected whether or not they continue with therapy or remain compliant (i.e. ITT principle). For survival analysis, if a subject is lost to follow up they will be censored at the last date for which the subject was known to be alive or free from the event. This means we assume non-informative censoring for lost to follow up. Here lost to follow up refers to conditional disengagement and early exit prior to study completion.

4.3.4 Sensitivity Analyses: LBBB Determination and aCRT Programming

As indicated in section **Error! Reference source not found.**, two sensitivity analyses will be performed for the primary objective. One is an ITT analysis of the randomized patients whose LBBB is confirmed by the ECG Core Lab. The purpose of this sensitivity analysis is to verify the effect of aCRT on the incidence of HF events or death among the true LBBB patients and to assess the impact of LBBB misclassification on the results. This analysis will be conducted in a similar way to that of the primary analysis:

```
PROC PHREG DATA=LBBB;  
CLASS NYHA site;  
MODEL time*event(0) = rand / TIES=efron;  
STRATA NYHA;  
RANDOM site/ dist = gamma;  
RUN;
```

Here, 'event', 'time' and 'aCRT' are defined in the same way as those in the primary analysis. A p-value for treatment below the cumulative α -level of approximately 0.00002, 0.00304, 0.0193 and 0.05 at the 1st, 2nd, 3rd interim and the final analysis, respectively, is significant.

The other sensitivity analysis will also be conducted in the randomized patients with ECG Core Lab confirmed LBBB, while the purpose is to verify the effect of aCRT on the primary endpoint based on the actual aCRT programming over time. Given this being said, this analysis will not follow the ITT principle and:

- Patients with major eligibility violations will be excluded (also when the violation becomes apparent only after randomization).
- Patients with major protocol violations after randomization, such as being programmed permanently to a mode that deviated from original randomization assignment due to a system modification after randomization, will be censored at the time of protocol violations.
- Patients' actual aCRT programming will be a time-varying covariate that has 3 categories: ACRT ON, ACRT OFF, and Neither, counting from the time randomization programming is implemented.

This analysis will be conducted using the following SAS PHREG procedure:

```
PROC PHREG DATA=LBBBCross COVSANDWICH (AGGREGATE) ;  
  ID pt;  
  CLASS NYHA site pt;  
  MODEL (start,stop)*event(0) = aCRTprog / TIES=efron;  
  STRATA NYHA;  
RUN;
```

where aCRTprog indicates patients' actual aCRT programming. Patients whose actual aCRT programming change over time get multiple records in the input dataset. Whenever there is a change, for instance, there will be one record in the randomized arm up until time of crossover and another record from time of crossover until the time that a primary endpoint is met or the time of censoring without meeting a primary endpoint. The COVSANDWICH option ensures the model accounts for multiple records coming from the same patient. In order to implement the COVSANDWICH option in SAS, random site effect will not be considered in this sensitivity analysis. A p-value for treatment below the cumulative α -level of approximately 0.00002, 0.00304, 0.0193 and 0.05 at the 1st, 2nd, 3rd interim and the final analysis, respectively, is significant.

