4 DESCRIPTION OF ANALYSIS

4.1 General

Medtronic employed statisticians will perform the statistical analyses described in this SAP. Interim analyses will be performed by a Medtronic statistician other than the lead statistician for the study. The lead study statistician will be blinded to all interim analyses.

All tests of treatment effects will be conducted in order to preserve an overall two-sided alpha level of 0.05 unless otherwise stated. An Intention-to-Treat analysis will be performed and will serve as the primary analysis for all objectives in this study. The Intention-to-Treat cohort will include all randomized subjects.

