4.1.2.3 Intention-to-treat and Sensitivity Analyses

An intention-to-treat (ITT) analysis will be performed and will serve as the primary analysis for all the objectives in this study. Based on the ITT principle, this analysis will include all randomized patients in the treatment groups to which they were randomly assigned, regardless of their adherence with the entry criteria, regardless of the treatment they actually received, and regardless of subsequent withdrawal from treatment or deviation from the protocol¹. With this being said, patients with noncompliance of randomization including permanent crossover to the other study arm will stay in the treatment arm they were originally randomized to in the primary ITT analysis. A permanent crossover means the programming will not be corrected to the original randomization assignment (CIP section 5.5).

In addition, two sensitivity analyses will be performed for the primary objective:

1. ITT analysis for randomized patients whose presence of LBBB is confirmed by the ECG Core Lab. In this sensitivity analysis, patients with noncompliance of randomization including permanent crossovers will stay in the treatment arm they were originally randomized to per the ITT principle.
2. As-treated analysis for randomized patients whose presence of LBBB is confirmed by the ECG Core Lab. In this sensitivity analysis, patients' actual aCRT programming will be a time-varying covariate that has 3 categories: ACRT ON, ACRT OFF, and Neither, counting from the time randomization programming is implemented. Patient with major eligibility violations discovered after randomization will be excluded. Patients with major protocol violations after randomization, such as being programmed permanently to a mode that deviated from original randomization assignment due to a system modification after randomization, will be censored at the time of protocol violations.

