4.2 Interim Analysis Plan

[figure not shown]
Four analyses including three interim analyses and a final analysis are planned for the primary objective. The 3 interim analyses will follow a symmetric group sequential design using the alpha-spending methodology of Lan and DeMets² with O'Brien-Fleming³ type boundaries. Specifically, the cumulative alpha-spending function at the k^{th} look or analysis:

$$\alpha(t_k) = 2 - 2\Phi\left(\frac{Z_{\alpha/2}}{\sqrt{t_k}}\right)$$

where $k=1, 2, \dots, K$ and t_k is the information fraction at the k^{th} look, In the group sequential design for time-to-event endpoint, the information fraction at the k^{th} look can be defined as the cumulative count of events at the k^{th} look divided by the projected number of events at the final look.

The O'Brien-Fleming function was chosen because it conservatively preserves most of the type I error for the final analysis, and the conservation of type I error is desired due to the multiple endpoints and objectives of interest in this trial. The statistical stopping rules are illustrated in the figure below.

Figure 1: Statistical stopping boundaries

The horizontal axis shows the number of events, indicating the timing of interim analyses after 275, 550, and 825 events, and the final analysis when 1100 events are accrued. If at any interim analysis the standardized Z statistic for the primary objective is in the darker blue area with solid boundary line, the DMC may advise to stop the study claiming the null hypothesis is rejected. This corresponds to a cumulative α -level of 0.00002, 0.00304, 0.0193 and 0.05 spent at the subsequent stages (see section 5.1 “Error Spending Information” table). If the Z Statistic is in the lighter blue area with dashed boundary line, the DMC may advise to stop the study for futility.

In case the study is stopped for efficacy after an interim analysis, the secondary objectives will be analyzed using a family-wise type I error rate derived from a Pocock-type alpha-spending function. This corresponds to a cumulative α -level of 0.018, 0.031, 0.041 and 0.05 spent at the subsequent stages⁴. Hommel procedure will be used to correct for multiplicity.⁵ This will be implemented by the SAS MULTTEST procedure.

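### SAP 4.3.4 lets two sensitivity analyses of the primary endpoint be called significant at the full alpha levels, with no gate on the ITT result and no multiplicity control

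*SAP*

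**What the plan says.** SAP 4.1 sets the general standard: "All tests of treatment effects will be conducted in order to preserve an overall two-sided alpha level of 0.05 unless otherwise stated". SAP 4.1.2.3 names the deciding analysis: "An intention-to-treat (ITT) analysis will be performed and will serve as the primary analysis for all the objectives in this study". SAP 4.3.2 then ties the conclusion to that model, concluding that "aCRT reduces the incidence of the primary endpoint when the null-hypothesis is rejected and the hazard ratio is below 1". Protocol 11.3.2 has the same rule.

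SAP 4.3.4 adds two sensitivity analyses of the same endpoint, both limited to patients whose LBBB the ECG Core Lab confirmed.

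- One compares the randomised arms. Its stated role is supportive: "The purpose of this sensitivity analysis is to verify the effect of aCRT on the incidence of HF events or death" in true LBBB patients.
- The other compares actual programming over time. By the SAP's own account it does not follow the ITT principle. It excludes major eligibility violators, including those found only after randomisation, and censors at major protocol violations.

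Each analysis closes with the same rule: a treatment p-value under 0.00002, 0.00304, "0.0193 and 0.05 at the 1st, 2nd, 3rd interim and the final analysis, respectively, is significant". These are the cumulative levels that SAP 4.2 lists for the primary test ("0.00002, 0.00304, 0.0193 and 0.05 spent at the subsequent stages").

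SAP 4.3.6 does the opposite for the covariate-adjusted ancillary analysis: it says that these critical values are not to be used there.

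**The concern.** The two rules stand alone. They are not conditional on rejecting the ITT null, and nothing orders or adjusts the three tests. The Hommel procedure (Protocol 11.5, SAP 4.4) covers only the secondary objectives, so these two tests fall outside every multiplicity control in the plan. Table 2 in SAP 4.1.3 puts the sensitivity analyses into each interim DMC report and the final report, so the label can be applied at all four looks.

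The practical risk is a narrow miss on the ITT test. The report could then describe a significant effect on the primary endpoint in confirmed LBBB, or by actual programming, and cite the SAP for the word.

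The as-treated rule is the weaker of the two. Randomisation does not protect that comparison, and Protocol 11.3.2 plans no such analysis. Its covariate also has three categories (ON, OFF, Neither), so a single treatment p-value is not uniquely defined.

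**Working it through.** **Inputs from the documents.** Overall two-sided alpha 0.05 (SAP 4.1); four equally spaced looks, hazard ratio 0.81818, 90% power, 1100 events (SAP 4.3.8); cumulative levels 0.00002, 0.00304, 0.0193, 0.05 (SAP 4.2); LBBB unconfirmed in 10% of patients (SAP 4.3.8).

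**Input not in the documents.** The correlation between the as-treated and confirmed-LBBB test statistics. I assume 0.80 to 0.99 and show the range.

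**1. The plan's own figures.** O'Brien-Fleming-type spending at 0.025 per side gives a two-sided cumulative alpha of 4{1 − Φ(2.2414/√t)}, where 2.2414 is the 0.9875 normal quantile.

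- t = 0.25: 4{1 − Φ(4.483)} = 0.000015
- t = 0.50: 4{1 − Φ(3.170)} = 0.00305
- t = 0.75: 4{1 − Φ(2.588)} = 0.0193
- t = 1: 4{1 − Φ(2.2414)} = 0.0500

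These match the listed levels to within 0.00001. The efficacy boundaries, ignoring futility, are Z = 4.333, 2.963, 2.359 and 2.014. With a matching futility boundary treated as binding, 90% power at hazard ratio 0.81818 needs 1102 events, against 1100 stated.

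**2. ITT test alone.** Its type I error over the four looks is 0.050.

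**3. Overlap of the tests.** A subset carrying a fraction f of the events has a test statistic correlated √f with the full-set statistic. With 10% unconfirmed and events in proportion to patients, the ITT to confirmed-LBBB correlation is √0.9 = 0.949. The ITT to as-treated correlation is taken as 0.949 times the assumed as-treated to confirmed-LBBB value.

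**4. Chance of a label under no effect.** I simulated 1 million null trials per setting, using the step 1 boundaries for all three analyses and following each trial until the ITT test stopped it or the final look was reached. ITT or confirmed LBBB gives 0.065, which needs no as-treated assumption. With the as-treated analysis added:

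| Assumed as-treated to confirmed-LBBB correlation | Any of three labelled | Sensitivity analysis labelled, ITT not | Same, favouring aCRT |
|---|---|---|---|
| 0.99 | 0.070 | 2.0% | 1.0% |
| 0.95 | 0.077 | 2.7% | 1.4% |
| 0.90 | 0.083 | 3.3% | 1.6% |
| 0.80 | 0.091 | 4.1% | 2.0% |

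**5. Variations.** With 5% unconfirmed and correlation 0.99, any of three is 0.065. With 20% unconfirmed and correlation 0.95, it is 0.083. If the listed levels are used literally as p-value cut-offs for the two sensitivity analyses, ITT or confirmed LBBB becomes 0.069, and any of three becomes 0.089 to 0.098 at correlations 0.90 to 0.80. Three independent tests would give 1 − 0.95³ = 0.143, but that does not apply here because the analyses share most of their patients and events.

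**The case against.** A reader might infer that the primary objective has three chances of success and that its 0.05 is lost. The documents do not support this. The conclusion rule (Protocol 11.3.2, SAP 4.3.2) belongs to the primary Cox model in all randomised patients. The efficacy boundary refers to one statistic: "If at any interim analysis the standardized Z statistic for the primary objective is in the darker blue area with solid boundary line". Protocol 5.1.1 calls the confirmed-LBBB analysis secondary, and the SAP calls both analyses sensitivity analyses. No section lets either one meet the primary objective, replace a failed ITT test or trigger an efficacy stop. This part of the objection stands in full.

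The size can also be argued down. A benefit conclusion needs a hazard ratio below 1, which halves the either-direction figures. Interim results go to the DMC, while the lead statistician and sponsor staff outside the unblinded interim team stay blinded (SAP 4.2). Counting only final-look labels that favour aCRT without ITT significance gives 1.4% to 1.7% at correlations 0.90 to 0.80, and 0.6% for confirmed LBBB alone. Censoring at protocol violations, as 4.3.4 prescribes for some deviations, pushes the as-treated correlation up and the figures down. This also stands, so the effect is small.

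It could further be said that 4.3.4 is the exception that the closing words of the SAP 4.1 sentence allow. That is weaker. Section 4.3.4 gives thresholds but nowhere says that the overall level is given up, and 4.3.6 shows that the authors wrote an explicit exemption when they meant one.

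**Conclusion.** The point holds as a defect in a stated reporting rule, not as an alpha error in the primary test. The type I error of the primary objective stays at 0.05. Two further analyses of the same endpoint, one of them not a randomised comparison, carry an uncontrolled significance label that conflicts with the general commitment in SAP 4.1.

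Under no effect, some label appears with probability 0.065 (ITT or confirmed LBBB) or about 0.070 to 0.091 (any of three). A sensitivity label without ITT significance appears in about 2.0% to 4.1% of null trials, or 1.0% to 2.0% in favour of aCRT. These are chances of a label, not error rates of the trial's decision.

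The figures rest on 10% unconfirmed LBBB, events in proportion to patients, the assumed correlation of 0.80 to 0.99, and an as-treated test of correct size, which confounding could worsen. This is a cheap improvement.

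**What to change.** Delete the closing significance sentence from both analyses in SAP 4.3.4. Report each as a hazard ratio with 95% confidence interval, describe both as supportive, and state that neither can establish the primary objective. If a formal claim in core-lab-confirmed LBBB is wanted, test that subset by randomised arm only after the ITT null has been rejected. Give the as-treated analysis no confirmatory threshold.

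The cost is wording only. The sponsor gives up a label that nothing controls, and the 1100 events, the power and the ITT boundaries are unchanged.
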